2. HYPOTHESIS

1. After 3 months, the intervention will improve the frequency and quality of primary and preventive care received by study participants in intervention sites compared to participants in sites with usual care.
2. After 3 months, the intervention will better integrate care between mental health services and general practice compared with usual care.
3. After 3 months, the intervention will improve consumer health risks and service use compared with usual care.
4. After 3 months, the intervention will demonstrate cost-effectiveness compared to usual care (i.e. the situation without the intervention) and *cost avoidance* (i.e. there will be reduced costs in the intervention group).

3. STUDY OBJECTIVES / AIMS

Aim: To investigate the adaptability, replicability and effectiveness of an online shared care plan in NSW Health mental health and primary care settings.

PRIMARY OBJECTIVES

Primary research question:

1. After 3 months, does the intervention improve the frequency and quality of **primary and preventive care** received by study participants in intervention sites compared to participants in sites with usual care?

SECONDARY OBJECTIVES

Secondary research questions:

2. After 3 months, does the intervention better integrate care between mental health services and general practice compared with usual care?
3. After 3 months, does the intervention improve consumer health risks and service use compared with usual care?
4. After 3 months, what are the main differences in the costs and various outcomes between the SHAReD intervention and usual care groups? If effectiveness has been demonstrated: is the SHAReD intervention more cost-effective compared to usual care, and are there any costs avoided due to the intervention?

4. STUDY DESIGN

4.1. DESIGN / STUDY TYPE

This is a pragmatic cluster randomised controlled trial. The unit of randomisation is the team. The teams are four of the five Adult Community Mental Health 'Core' Teams in SLHD (Table 1). Randomisation will be stratified by sector (Eastern and Western): One team from each sector will be randomised to the intervention group, the other team will be allocated to the comparison group. The comparison group Teams will receive the intervention after the 3-month data collection is complete.

As there are only two teams per sector in the study, randomisation will be done by a person independent from the study by flipping a coin.

4.2. EXPECTED PARTICIPANT NUMBERS

We aim to recruit 500 consumers and expect 400 to remain in the study at 3-month follow-up (20% loss to follow up). Power calculation: Assuming 20% change in the frequency and quality of primary and preventative care received by participants, a sample size of 91 per group is required to detect a change from 30 to 50% in primary outcomes based on $\alpha = 0.05$, $1-\beta = 0.8$. Assuming a design effect due to clustering of 2, a total sample of 360 is required (180 in each group).

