
Study Procedure
	
 1.SLHD Adult Community Mental Health 'Core' Teams will be randomised to – 1 of Canterbury or Croydon and 1 of Camperdown or Marrickville will be randomly allocated to the intervention group and the other will receive delayed intervention 2.500 People with severe mental illness (PWSMI) who have contact with these teams and who are identified as suitable by the Core team staff member who is their care coordinator during routine visits will be given written information about the study. With the consumer’s permission, care coordinators will provide the research team with contact details of consumers who are interested in participating in the study. 3.A research officer will contact these potential participants to explain the study, answer any questions, and obtain informed consent. 4.Participant consumers will be asked to approach their GP to be part of the project OR consent to the research team doing so on their behalf to recruit GPs to the study. 5.If GPs provide consent to participate in the study, they and their patient are enrolled in the study and an appointment is made to install the INCA shared care software in the GP practice’s computer and arrangements will be made to train the GP in its use and a baseline survey is conducted with the consumers and their shared-care GPs. 6.Consumers in the intervention group will have their physical health care coordinated through an online shared care plan. 7.Consumers in the comparison group will receive usual care. 8.If GPs withdrew consent to participate in the study, their patient will remain enrolled in the study and will be able to participate in a repeat interview 3 months after their reported usual shared care. 9.Consumer and GP participants will participate in a repeat interview 3 months after their reported usual shared care. If any consumer does not have a shared care appointment/follow-up since baseline, they will be invited to participate in the repeated interview three months after 30 June 2023 (i.e., 3 months after the deadline for the intervention to be implemented). 10.With consent and approval, relevant health service use and clinical data will be extracted from medical records held by GPs, datasets held by SLHD, HealthNet (including MBS/PBS items), and the NSW Ministry of Health (ICOD). 11.A subset of consumers will be invited to participate in a qualitative interview after 3 months of their reported usual shared care. 12.A subset of SLHD mental health clinicians (Care Coordinators and shared care clinicians) and GPs will be interviewed after the intervention period.

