5. GPs can consent verbally (Appendix 11.6) or by signing a written consent form (Appendix 11.3). GPs will be offered reimbursement for their participation in the study (\$100 shopping voucher or cash for participating in each component of the study). Recruitment materials include a letter of invitation from the head of the mental health service in the LHD (Appendix 15.1), a letter from the GP's patient informing the GP that s/he has consented to be in the study and inviting the GP to also consent to be in the study (Appendix 15.2), GP participant information abbreviated (Appendix 15.3) and in full (Appendix 10.2).

9. *What happens if a GP does not want to participate?*

If a GP does not want to participate in the trial, neither they nor their patients who are engaged with the mental health service (MHS) will be given access to the online shared-care tool. Consumers of these GPs can still provide baseline data for the study and will be followed up for the study. Communication between the GP and the MHS will continue as usual, which is generally via letters and faxes.

10. How will participants be recruited to the qualitative interview?

Participants from both groups will be invited to participate in semi-structured qualitative interviews. This will include consumers and their carers, and health care providers (including MHS staff and GPs).

Consumers will be invited to express interest in themselves and/or their carers being interviewed for the study via an invitation within the consumer survey. Contact details will be requested so the study team can contact the consumer and/or their carer.

The research team will contact the consumers who expressed interest and any carers who were nominated by consumers to recruit them to the qualitative interviews.

GPs will be invited to express interest in being interviewed for the study via an invitation within the GP survey. A similar process to that for consumers will be used to contact those GPs who expressed interest in being interviewed.

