8.2. PROVIDE A DETAILED ANALYSIS PLAN

Quantitative analysis

The fidelity and tailoring of the intervention to participants' needs will be assessed by analysing records, provider and consumer interviews 3 months after their usual shared care appointments. We will compare outcomes over 3 months after intervention between SHAReD intervention and comparison groups with linear or generalised multi-level mixed models including age, sex and key independent variables that are found to be significantly different between groups at baseline. Intra-class correlations will be calculated to compare the amount of variance associated with design features such as individual participants nested within care coordinators who are nested within community mental health teams, and those same participants are also nested within GPs who could also be nested within medical centres, before selecting random effects for these statistical models. As well as an analysis of completers (defined as those consumers, care coordinator and GP who

consented and are engaged in shared care), an intention to treat (ITT) analysis will also be included for this project. For the ITT analysis, those who drop out of the study (defined as consumers who were discharged of shared care or who withdrew consent) will be treated using a variety of sensitivity analyses including multiple imputation for the missing values on key measures resulting from them dropping out of the study. Sensitivity analyses will assess unmeasured variation.

Qualitative analyses

This will evaluate the experience of participants, carers and providers, barriers to implementation, conditions for sustainability and translation. Qualitative data will be managed and coded using NVivo 11 analysis software (QSR International). Two researchers will review each transcript and develop coding aligned with the Theoretical Domains Framework and Normalisation Process Theory.^{25,26} Coding will be predominantly deductive but inductive coding will also be applied to detect new and emerging themes.

Data combining and cost analyses

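### The 80% power makes no allowance for intervention-site consumers without the online plan, and the protocol is inconsistent about whether they are enrolled and analysed

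*Protocol*

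**What the plan says.** **Sizing.** Section 4.2 states "Assuming 20% change in the frequency and quality of primary and preventative care received by participants, a sample size of 91 per group is required", with 30% versus 50% in the primary outcomes as the target difference, at 5% significance and 80% power, then "Assuming a design effect due to clustering of 2, a total sample of 360 is required (180 in each group". It plans to recruit 500 and expects 400 at follow-up. The synopsis and section 8.1 repeat the calculation. None of the three has a term for intervention-site consumers who cannot use the online plan.

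**Consumers without a participating GP.** The protocol gives two accounts.

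- Kept and followed. Section 5.3, on GPs who do not want to take part: "neither they nor their patients who are engaged with the mental health service (MHS) will be given access to the online shared-care tool". It continues: "Consumers of these GPs can still provide baseline data for the study and will be followed up for the study". Communication for these consumers stays as usual, by letter and fax. Synopsis, Study Procedure item 8: "If GPs withdrew consent to participate in the study, their patient will remain enrolled in the study".
- Not eligible, or not mentioned. Criterion 4 (synopsis and section 5.1) requires intervention-group consumers to have a GP who consents and has the plan installed. Section 6.5 enrols only people who meet every inclusion criterion. Section 4.5 ties enrolment in the intervention group to GP consent, and states ITT retention after GP refusal for the comparison group only.

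**Analysis.** Section 8.2 describes a completer analysis and adds that "an intention to treat (ITT) analysis will also be included for this project". It names neither as primary. Drop-outs are defined as consumers discharged from shared care or who withdrew consent.

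**The concern.** The primary question in section 3 compares participants at intervention sites with participants at usual-care sites, and randomisation is by team. Table 9 defines the intervention as having a shared care plan in the software. An intervention-site consumer whose GP declines has no such plan, so including that consumer pulls the arm's result towards usual care.

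The 20% loss allowance does not cover this. A consumer with a declining GP is neither discharged from shared care nor withdrawn. Such consumers are followed up and so count among the 400. Table 8 lists GP refusal as a risk but gives no rate.

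At stake is whether the stated 80% applies to the randomised comparison. If it applies only to consumers who receive the plan, the ITT comparison has less power than the protocol reports. If criterion 4 governs instead, intervention consumers are selected on GP consent and comparison consumers are not, which weakens the comparability that randomisation provides.

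**Working it through.** **Inputs.** From section 4.2: rates 0.30 and 0.50, α = 0.05 (taken as two-sided, which reproduces the plan's figure), power 0.80, design effect 2, 180 per group, 400 retained (200 per group if split equally). Not in the protocol: q, the share of analysed intervention-arm consumers whose GP takes part. A range is used.

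**Step 1: reproduce the plan.** Unpooled two-proportion formula:

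n = (1.96 + 0.8416)² × (0.30×0.70 + 0.50×0.50) / 0.20² = 7.849 × 0.46 / 0.04 = 90.3, rounded up to 91 per group. This matches the protocol.

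With design effect 2: 4 × 91 = 364 in total, against the stated 360. The difference is rounding.

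**Step 2: margin with full access.** Power = Φ(Δ / SE − 1.96), with SE = √[(p₁(1−p₁) + p₂(1−p₂)) / n_eff] and n_eff = n / 2.

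- 180 per group (n_eff = 90): SE = √(0.46/90) = 0.0715; 0.20/0.0715 − 1.96 = 0.84; power 80%.
- 200 per group (n_eff = 100): SE = 0.0678; 0.20/0.0678 − 1.96 = 0.99; power 84%.

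So there is no margin at 180 per group and about four points at 200.

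**Step 3: allow for lack of access.** Assume that consumers without the plan are analysed as randomised, that 20 points is the effect among recipients, and that the effect without the tool is zero. The intervention-arm rate becomes 0.30 + 0.20q.

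Example, q = 0.9, 180 per group: p₂ = 0.48, Δ = 0.18, SE = √[(0.21 + 0.2496)/90] = 0.0715; 0.18/0.0715 − 1.96 = 0.56; power 71%.

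| q | Rates compared | Power, 180 per group | Power, 200 per group |
|---|---|---|---|
| 1.00 | 30% vs 50% | 80% | 84% |
| 0.95 | 30% vs 49% | 76% | 80% |
| 0.90 | 30% vs 48% | 71% | 76% |
| 0.80 | 30% vs 46% | 61% | 66% |
| 0.70 | 30% vs 44% | 50% | 55% |
| 0.50 | 30% vs 40% | 29% | 32% |

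**Step 4: sensitivity to the formula.** The pooled-variance version gives values about one point lower: at q = 0.9, 70% and 75%; at q = 0.8, 60% and 65%; at q = 0.7, 49% and 54%. With 400 retained, power crosses 80% at about 4% without access (pooled) or 5% (unpooled).

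**The case against.** The 91 and, within rounding, the 360 reproduce, so there is no arithmetic error. A reader might go further and infer that the sizing assumes the full effect in every intervention consumer and that power is therefore well below the claim. The protocol does not support that, for four reasons.

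1. Section 4.2 refers to care received by participants, and section 3 compares participants by site. Both can be read as arm-level. If the 20 points is already net of GP refusal, multiplying by q discounts it twice.
2. Retention in the ITT analysis after GP refusal is explicit only for the comparison group. For the intervention group it is inferred from section 5.3, synopsis item 8 and section 8.2, against criterion 4 and section 4.5. If criterion 4 governs, dilution comes only from GPs who withdraw later, and the protocol does not spell out whether their patients lose access.
3. No value of q is given. At q = 0.95 with 400 retained, power is still about 80%.
4. Zero effect without the tool is a worst case. Training and redesign of routine practice also reach the mental health teams (section 1.1), and section 5.3 notes that consumers change GPs.

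The figures also come from an unadjusted two-proportion test, not the multilevel models of section 8.2, so they are illustrative.

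All of this stands, and it makes the size of any shortfall conditional. It does not remove the missing allowance or the contradiction over who is enrolled. Nor does it make the question idle now that recruitment is over: the ITT set still has to be fixed before analysis, and readers will interpret a null ITT result against the stated power.

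**Conclusion.** The point holds in conditional form. The sizing allows for clustering and 20% loss only. It fits a population in which every intervention consumer has a consenting GP, while other parts of the protocol keep and follow consumers whose GP declines or withdraws.

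Under the three assumptions in Step 3, 10% without access already takes power to 70–71% at 180 per group and 75–76% at 200. At 20% without access it is 60–61% and 65–66%. At 5% or less with 400 retained, the loss is negligible. Since the protocol gives no participation share and does not say which effect the 20 points describes, a shortfall is possible but not established.

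The contradiction over the intervention-arm ITT set needs no assumption and must be resolved in any case.

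**What to change.** 1. Reconcile synopsis item 8, section 4.5, criterion 4 (synopsis and section 5.1) and section 5.3, so that the ITT set is all consenting consumers of the randomised teams in both arms, regardless of GP consent.
2. In the synopsis, 4.2 and 8.1, say whether 30% versus 50% is the arm-level effect or the effect among consumers who receive the online plan.
3. If it is the recipient-level effect, restate ITT power as 30% versus (30 + 20q)%. Use the expected q, the observed q (Table 2 ends recruitment in 12/2022, so it may be known), or a range. If it is arm-level, one sentence saying that it already allows for GP non-participation is enough.

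The cost is rewording and one recalculation. No extra enrolment is needed. If the effect is recipient-level, the stated power becomes less favourable.

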4.4. ENDPOINTS

PRIMARY ENDPOINTS

Differences between the intervention and comparison groups in changes in the frequency and quality of preventive care from their reported usual shared care to 3-months:

1. Increased % of consumers for whom each health risk is measured and recorded over the preceding 3 months*
2. Increased % consumers who have been vaccinated against influenza over the preceding 3 months
3. Decreased % consumers with high CVD risk who have not received a prescription for either an anti-hypertensive or lipid lowering drug.
4. Increased % consumers who report advice/referral for smoking cessation, diet education and physical activity over the preceding 3 months.

* Health risks are itemised in Table 3.

SECONDARY ENDPOINTS

Differences between the intervention and comparison groups in changes from their reported usual shared care to 3-months:

5. Increased % MHS consumers have a care plan (GPMP and TCA) in last 3 months
6. Increased consumer rating of extent to which providers (MH & GP) are working to a common care plan in the past 3 months
7. Improved quality of communication between MHSs and GPs in last 3 months
8. Reduced number of ED attendances and hospitalisations in last 3 months
9. Increased number of visits to GP in last 3 months
10. Improved consumer experience of providers (MH & GP) working to a common (shared) care plan in the past 3 months (qualitative analysis)
11. Increased scores on Domain 1 (Feeling understood and supported by healthcare providers) and Domain 7 (Navigating the healthcare system) of the Health Literacy Questionnaire
12. Increased score on Patient Activation Measure (PAM-13)
13. Improved diet and physical activity behaviours
14. Reduced Absolute Cardiovascular Disease Risk score **
15. Reduced diabetes risk score using AUSDRISK ***
16. Improved levels of most recently recorded results from health risk screening*
17. Reduced costs of hospitalisations in last 3 months
18. Reduced out of pocket costs of participants
19. Improvements in Quality of Life as assessed by the EQ5D-5L.

* Health risks are itemised in Table 3.

** Information needed for CVD risk score is provided in Table 4

*** Information needed for AUSDRISK score is provided in Table 5.

Table 3 Health risks

Health risks	Units/options	Normal range/goals
Systolic & diastolic blood pressure (BP)	mmHg	<130/85 mm Hg

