5. STUDY PARTICIPANTS

5.1. INCLUSION CRITERIA

1. Consumers from SLHD Adult Community Mental Health 'Core' Teams in Canterbury, Croydon, Camperdown and Marrickville.
2. Age: 18+ years
3. Engaged in shared care or willing to commence a shared care arrangement before the baseline survey.
4. Intervention group: Has a GP engaged in shared care who consents to participate in the study and to have the electronic care plan installed
5. Willing to provide informed consent and willingness to participate and comply with the study requirements.

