8. STATISTICAL CONSIDERATIONS

8.1. SAMPLE SIZE OR POWER CALCULATION

We aim to recruit 500 consumers and expect 400 to remain in the study at 9-month follow-up (20% loss to follow up). Power calculation: Assuming 20% change, a sample size of 91 per group is required to detect a change from 30 to 50% in primary outcomes based on $\alpha = 0.05$, $1-\beta = 0.8$. Assuming a design effect due to clustering of 2, a total sample of 360 is required (180 in each group).

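### The 80% power stated for the primary outcomes as a set does not carry over to primary endpoint 3 if, as section 4.4 says, only consumers with high CVD risk are counted

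*Protocol*

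**What the plan says.** Section 4.2 gives one power calculation for all the primary outcomes together: "a sample size of 91 per group is required to detect a change from 30 to 50% in primary outcomes", with a significance level of 0.05 and power of 0.8. It continues: "Assuming a design effect due to clustering of 2, a total sample of 360 is required (180 in each group"). Section 8.1 ends on the same figure, "a total sample of 360 is required (180 in each group"), and the synopsis repeats it. On recruitment, section 4.2 says: "We aim to recruit 500 consumers and expect 400 to remain in the study at 3-month follow-up (20% loss to follow up").

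Section 4.4 lists four primary endpoints. The third is: "Decreased % consumers with high CVD risk who have not received a prescription for either an anti-hypertensive or lipid lowering drug".

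Entry is not limited by cardiovascular risk. Section 5.1 admits "Consumers from SLHD Adult Community Mental Health 'Core' Teams in Canterbury, Croydon, Camperdown and Marrickville", subject to age, shared-care, GP (intervention group) and consent conditions. Section 5.2 adds no CVD-risk exclusion.

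Table 9 in section 7 lists GP-recorded prescribing of antihypertensive or lipid-lowering drugs as a primary outcome and mentions no restriction to high-risk consumers. The protocol nowhere gives the expected share or number of consumers at high CVD risk, or a separate power figure for this endpoint.

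**The concern.** A calculation for two proportions gives the stated power only if the stated number of people enter each proportion. Under section 4.4, endpoint 3 uses 180 multiplied by the share at high CVD risk, not 180. The calculation makes no allowance for that share, yet its result is given for the primary outcomes as a group.

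At stake is how the prescribing result is read. A reader who takes 80% from section 4.2 would credit the trial with more ability to detect a 20-point difference in this endpoint than it has on the plan's own assumptions.

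**Working it through.** **Inputs from the protocol.** Proportions of 30% and 50%, alpha 0.05, power 0.8, design effect 2, and 180 per group (section 4.2). Expected retention is 400, so about 200 per group. Allocation is two teams against two: "One team from each sector will be randomised to the intervention group, the other team will be allocated to the comparison group" (section 4.1).

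**Inputs assumed.** A two-sided test, because that reproduces the stated figure. The high-risk share f, which the protocol does not give, is taken over a range. For the scaled clustering calculation, the design effect of 2 is taken to refer to teams of 90 (180 per group over two teams), which gives ICC = (2 − 1)/(90 − 1) = 1/89.

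**Reproducing the plan's figure.** With unpooled variance, n = (1.960 + 0.842)² × (0.3×0.7 + 0.5×0.5)/0.20² = 90.3, rounded up to 91. Doubling gives 182 per group; the plan prints 180, which is within rounding. The power at 180 per group with design effect 2 is Φ(0.20/√(0.46/90) − 1.96) = 79.9%. The stated figures are therefore right when every consumer counts.

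**Endpoint 3 on the section 4.4 wording.** Power = Φ(0.20/√(0.46/n_eff) − 1.96), with N analysed per group and:

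- design effect held at 2: n_eff = N·f/2
- design effect scaled to the smaller clusters: n_eff = N·f/(1 + (N·f/2 − 1)/89)

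At N = 180:

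| f (assumed) | High-risk per group | n_eff, held at 2 | Power | n_eff, scaled | Power |
|---|---|---|---|---|---|
| 0.2 | 36 | 18.0 | 24% | 30.2 | 37% |
| 0.4 | 72 | 36.0 | 42% | 51.7 | 56% |
| 0.6 | 108 | 54.0 | 58% | 67.7 | 68% |
| 0.8 | 144 | 72.0 | 71% | 80.1 | 75% |

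At N = 200:

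- f = 0.4: n_eff is 40.0 to 55.6, and power is 46% to 59%.
- f = 0.8: n_eff is 80.0 to 84.8, and power is 75% to 77%.

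**Break-even.** n_eff must be about 90.3. At N = 180 with design effect 2 this needs f = 2×90.3/180, or 1.0. At N = 200 it needs f = 2×90.3/200 = 0.90, and the scaled version gives nearly the same value.

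**Sensitivity.**

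- If the design effect of 2 is instead attached to teams of 100 (ICC 1/99), power at N = 200 is 61% at f = 0.4 and 79% at f = 0.8. The break-even f is then 90.3×(98/99)/(1 − 90.3/198)/200, about 0.82.
- The pooled-variance formula gives slightly lower power throughout (78.7% rather than 79.9% at f = 1 and N = 180).
- Framing endpoint 3 as a decrease changes nothing: 50% to 30% and 70% to 50% have the same variances as 30% to 50%.

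**The case against.** The strongest objection is that the denominator is not settled. Table 9 names the prescribing outcome with no high-risk restriction, and if that wording governs, every consumer counts and the shortfall disappears. This stands, and it makes the point conditional. But section 4.4 is where the endpoints are defined, and its current text carries the restriction, so one of the two places has to change.

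Section 4.4 could also be read as the share of all consumers who are both high risk and untreated. That does not rescue the power statement. Such a share cannot exceed f, so a fall from 50% to 30% needs f of at least 0.5 and a fall from 70% to 50% needs at least 0.7. The generic scenario still depends on a share that is not stated.

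It may be said that power by endpoint belongs in a SAP that is not shown. The point is not that detail is absent. It is that a statement the protocol does make, for its primary outcomes as a group, does not follow for one of them.

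Three stronger readings are tempting and not supported:

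- A reader might infer that the sample-size arithmetic is wrong. It is not: 91 reproduces, and 180 is within rounding.
- A reader might infer a guaranteed minimum loss, such as about 5 points for any f up to 0.8. That holds at 180 per group, but at the expected 200 per group with a scaled design effect the loss at f = 0.8 is only about 2.5 points.
- A reader might infer that endpoint 3 should become secondary. Table 2 ends recruitment in December 2022 and version 11 is dated October 2023, so demotion for low power at that stage would invite criticism for outcome switching.

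**Conclusion.** The point holds, conditionally. If the section 4.4 wording governs, the printed 80% does not apply to primary endpoint 3 unless about 90% or more of consumers are at high CVD risk (about 82% under the most lenient clustering assumption tried). The direction does not depend on the exact share when f is clearly below that level, but the size does. For f between 0.2 and 0.8, power at 180 per group runs from 24% to 75%. At the expected 200 per group it is roughly 46% to 60% at f = 0.4 and up to about 77% at f = 0.8.

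These figures take the plan's 20-point difference and design effect of 2 as given. The lower value in each range holds the design effect at 2 although the clusters are smaller, which is pessimistic. The upper value assumes that it refers to teams of 90, which the protocol does not say. Nothing here affects endpoints whose denominator is all consumers.

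**What to change.** 1. Reconcile section 4.4 with Table 9, so that the prescribing outcome has one stated denominator.
2. If the high-risk restriction stays, limit the 80% statement in section 4.2, section 8.1 and the synopsis to primary endpoints whose denominator is all consumers. For endpoint 3, state the expected number of high-risk consumers per group and the resulting power or detectable difference, with the clustering assumption used.
3. If Table 9's unrestricted wording is the intended one, amend endpoint 3 in section 4.4 to match. The general power statement then needs no exception on this account.

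The endpoint should not be demoted and no more consumers need be enrolled. The cost is wording and, if the restriction stays, one recalculation and a less favourable power printed for one endpoint.

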7. OUTCOMES AND DATA SOURCES

Table 9 Outcomes and their data sources

Concept	Primary Outcomes	Data source
1 Preventive care	GP-recorded screening of health risks 6-month period post-intervention* (May-October 2023) compared with the 6-month periods: 
 • Pre-intervention (November 2022-April 2023) • In the previous year (May-October 2022) 
*"intervention" = shard care plan in Inca (May-June 2023)
	GP records
	GP-recorded prescription of antihypertensive or lipid lower medications 6-month period post-intervention* (May-October 2023) compared with the 6-month periods: 
 • Pre-intervention (November 2022-April 2023) • In the previous year (May-October 2022) 
*"intervention" = shard care plan in Inca (May-June 2023)
	GP records & HealtheNet
	Consumer-reported advice/referral from GP for smoking cessation, diet and physical activity in last 6 months	Consumer survey

Concept	Secondary Outcomes	Data source
1 Preventive care	GP-recorded care plans: GPNP and Team Care, mental health 6-month period post-intervention* (May-October 2023) compared with the 6-month periods: 
 • Pre-intervention (November 2022-April 2023) • In the previous year (May-October 2022) 
*"intervention" = shard care plan in Inca (May-June 2023)
	GP records
2 Integration of care	Consumer assessment of extent to which providers (MH & GP) are working to a common care plan in last 6 months	Consumer survey
	Provider reported quality of communication between MHSs and GPs in last 6 months	Provider survey and qualitative interviews

Concept	Secondary Outcomes	Data source
3 Health service use	ED use and hospitalisations for primary care preventable conditions and other conditions 6-month period post-intervention* (May-October 2023) compared with the 6-month periods: 
 • Pre-intervention (November 2022-April 2023) • In the previous year (May-October 2022, to check for seasonal effect) 
*"intervention" = shard care plan in Inca (May-June 2023)
	SLHD eMR (Appendix 14), Integrated Care Outcomes Database (ICOD)

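### The stated 80% power belongs to a comparison of follow-up percentages, but section 4.4 names the primary endpoints as differences in change, and for those no power is established

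*Protocol*

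**What the plan says.** The power statement in section 4.2 reads "a sample size of 91 per group is required to detect a change from 30 to 50% in primary outcomes", at alpha 0.05 and 80% power. It continues: "Assuming a design effect due to clustering of 2, a total sample of 360 is required (180 in each group". Section 8.1 and the synopsis repeat these numbers. On recruitment, 4.2 says "We aim to recruit 500 consumers and expect 400 to remain in the study at 3-month follow-up (20% loss to follow up".

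Section 4.4 introduces all four primary endpoints with "Differences between the intervention and comparison groups in changes in the frequency and quality of preventive care from their reported usual shared care to 3-months". Table 9 in section 7 sets the GP-recorded primary outcomes against earlier periods; the screening outcome, for example, is "GP-recorded screening of health risks 6-month period post-intervention* (May-October 2023) compared with the 6-month periods" before the intervention and in the same months of the previous year.

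Section 8.2 plans mixed models that compare post-intervention outcomes between the two groups. The covariates are age, sex and variables found to differ significantly between groups at baseline. It names no change-score or group-by-time test for the primary endpoints. No within-consumer correlation appears anywhere in the protocol.

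**The concern.** A difference in change is not the same contrast as a difference at follow-up. It carries the sampling error of four percentages instead of two, and only the correlation between the two periods brings that error down. If the correlation is low, the change contrast is less precise than the follow-up contrast; if it is high, more precise. A power statement for one therefore says nothing definite about the other.

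The sections do not name one contrast: 4.2, 8.1 and 8.2 fit a comparison at follow-up, while 4.4 and Table 9 describe change. At stake is whether the 80% printed in three places is a property of the primary endpoints as 4.4 defines them.

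**Working it through.** **Inputs.** From 4.2, 8.1 and the synopsis: 30% and 50%, alpha 0.05 (sidedness not stated; two-sided reproduces), power 0.80, 91 per group, design effect 2, 180 per group and 360 in total. From 4.2: 400 expected at follow-up. Not in the protocol, so assumed here: both arms start at 30% and the comparison arm stays there; a correlation r between the two periods, the same in both arms; and, at first, an unchanged design effect of 2 for a change contrast.

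**1. The plan's own figure.** (1.960 + 0.842)² = 7.849. Per group, n = 7.849 × (0.30×0.70 + 0.50×0.50) / 0.20² = 7.849 × 0.46 / 0.04 = 90.3, rounded up to 91. (The pooled-variance formula gives 93.) The formula has no baseline term. Doubling gives 182 per group and 364 in total, against 180 and 360 stated.

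**2. Power of the follow-up contrast.** The effective number per group is 180/2 = 90, or 200/2 = 100 with 400 followed up. Power = Φ(0.20/√(0.46/n) − 1.96).
- n = 90: Φ(2.798 − 1.960) = 80%
- n = 100: Φ(2.949 − 1.960) = 84%

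The pooled formula gives 79% and 83%. No correlation is needed.

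**3. Power of an unadjusted difference in change.** The per-consumer variance of change is 0.42(1 − r) in the comparison arm and 0.21 + 0.25 − 2r√(0.21×0.25) = 0.46 − 0.458r in the intervention arm. The sum is V(r) = 0.88 − 0.878r. Power = Φ(0.20/√(V/n) − 1.96).

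| r | V(r) | Power, 360 (n = 90) | Power, 400 (n = 100) |
|---|---|---|---|
| 0 | 0.880 | 52.5% | 56.8% |
| 0.2 | 0.704 | 61.8% | 66.4% |
| 0.3 | 0.617 | 67.6% | 72.1% |
| 0.4 | 0.529 | 74.2% | 78.5% |
| 0.5 | 0.441 | 81.5% | 85.4% |

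For 80% power V must fall to n × 0.04/7.849, which is 0.459 at n = 90 and 0.510 at n = 100. Solving, r = (0.88 − 0.459)/0.878 = 0.48 and r = (0.88 − 0.510)/0.878 = 0.42.

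**4. How far the design-effect assumption matters.** With two equal teams per arm, 180 per group is 90 per team, and a design effect of 2 means 1 + 89 × ICC = 2, so ICC = 1/89. Let π be the correlation of team effects over time and s the consumer's correlation within team. The correlation that matters for the arm means is [90 × ICC × π + (1 − ICC) × s]/2 ≈ 0.506π + 0.494s. Step 3 in effect sets π = s. With s = 0, π = 0.8 gives r = 0.40 and about 75% power at 360; π = 1 gives r = 0.51 and about 82%. With 400 followed up these become about 79% and 86%. In the other direction, π = 0.25 would need s of about 0.72 to reach r = 0.48. Neither π nor s is in the protocol.

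**5. Follow-up contrast adjusted for the baseline outcome.** On the usual linear approximation the required number is multiplied by (1 − r²): 91 at r = 0, 82.8 at 0.3 and 70.0 at 0.48. It never exceeds 91.

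**The case against.** The strongest reply is that 8.2 is the analysis section and compares outcomes after the intervention between groups, which is what 30% against 50% powers. The hypotheses and research questions in sections 2 and 3 are also framed as group comparisons after 3 months, and how change is modelled may be left to an SAP. This stands in part: for that contrast the calculation is sound. But it leaves 4.4 naming a different primary contrast within the same document. Nor does 8.2 secure adjustment for the baseline value of the outcome, because that enters only if it happens to differ significantly between groups.

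A reader might infer that the trial needs a correlation of 0.48, or that it is underpowered outright. The documents do not support that. The 0.48 applies only to an unadjusted change contrast at 360; it is 0.42 at the expected 400, and it depends on carrying the design effect of 2 over unchanged, although stable team differences cancel in a change.

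A reader might also argue that care on an annual cycle pushes the correlation to zero or below. The protocol does not establish this: Table 9 also compares with the same months of the previous year, where an annual cycle would raise the correlation, and prescribing may well persist between periods.

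Finally, a reader might treat 360 instead of 364 as an error that matters. It is a rounding of about 1%, covered by the 400 expected at follow-up, and is not a reason to act.

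**Conclusion.** The point holds as a mismatch between the primary endpoint and the power statement. The 80% is right for a comparison of follow-up percentages (about 80% at 360, 84% at 400) and is not established for the difference in change that 4.4 calls primary. If an unadjusted change were analysed, power at correlations from 0 to 0.3 would be about 53% to 68% with 360, or 57% to 72% with 400, and would reach 80% at 0.48 or 0.42.

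Those values rest on three assumptions that the protocol does not state: the comparison arm stays at 30%, one correlation applies throughout, and the design effect of 2 carries over. With stable team differences the loss shrinks and can vanish. The calculations use the plan's own large-sample approach with a design effect; they do not address the small number of teams, which is a separate matter.

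**What to change.** Choose one of two routes.

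- **Follow-up contrast.** State in 4.4 that the primary contrast is the percentage at follow-up compared between groups, and in 8.2 that the model adjusts for the same outcome in a named baseline period, whether or not the groups differ on it. The power statement then fits, and the required number does not rise.
- **Difference in change.** Keep 4.4, have 8.2 name the test of change, and restate the power in 4.2, 8.1 and the synopsis over a stated range of correlations (for example 0 to 0.5), with the assumed comparison-arm percentage and the design effect used for change.

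The first route costs wording only. The second costs a power figure that is less favourable over much of that range. Neither requires more consumers to be recruited.
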